10.3.3.3.2. Proportion of SPT area of wounds treated per procedure

For the multiple imputation outlined in Section 10.1.1.3 information on the proportion of the SPT area of wounds treated per procedure will be computed using the following formula:

$$Prop(SPT) = \frac{\sum_i \%SPT(W_i) * \%TBSA(W_i)}{\sum_i \%TBSA(W_i)},$$

where both sums range over all target wounds treated in a debridement procedure, $\%SPT(W_i)$ is the percent area of SPT of target wound i and $\%TBSA(W_i)$ is the area of the target wound i . $Prop(SPT)$ will be computed for each procedure in each patient separately.

10.3.3.3.3. Proportion of DPT area of wounds treated per procedure

For the multiple imputation outlined in Section 10.1.1.3 information on the proportion of the DPT area of wounds treated per procedure will be computed using the following formula:

$$Prop(DPT) = \frac{\sum_i \%DPT(W_i) * \%TBSA(W_i)}{\sum_i \%TBSA(W_i)},$$

where both sums range over all target wounds treated in a debridement procedure, $\%DPT(W_i)$ is the percent area of DPT of target wound i and $\%TBSA(W_i)$ is the area of the target wound i . $Prop(DPT)$ will be computed for each procedure in each patient separately.

10.3.3.3.4. Proportion of FT area of wounds treated per procedure

For the multiple imputation outlined in Section 10.1.1.3 information on the proportion of the FT area of wounds treated per procedure will be computed using the following formula:

$$Prop(FT) = \frac{\sum_i \%DPT(W_i) * \%TBSA(W_i)}{\sum_i \%TBSA(W_i)},$$

where both sums range over all target wounds treated in a debridement procedure, $\%FT(W_i)$ is the percent area of FT of target wound i and $\%TBSA(W_i)$ is the area of the target wound i . $Prop(FT)$ will be computed for each procedure in each patient separately.

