10.1.1.3. Secondary Endpoint: Blood loss

Missing blood loss values for some eschar removal procedures may occur within a certain patient. A regression model containing main prognostic factors (wound area, depth of wound and type of procedure) for blood loss of eschar removal procedures will be computed on a procedure level treating all procedures as independent. On this basis a multiple imputation will be calculated. The procedure can be described as follows:

1. Test for normality: The Shapiro-Wilk test will be performed on the dataset of non-missing values in each treatment group. The result of these tests will determine the type of the analysis on the imputed data sets (step 3). If the normal distribution hypothesis is not rejected at the 5% significance level in either group, then differences in distribution between NexoBrid and SOC will be tested using a t-test. If the normal distribution hypothesis is rejected either in the NexoBrid group or in the SOC group, then the differences in distribution between the treatment groups will be tested using a Mann-Whitney test.
2. Imputation: Fit a linear regression model with target variable blood loss on a procedure level (as computed in Section 10.3.3.3) and dependent variables size of wounds treated in this procedure (wound area), proportion of area SPT of wounds treated in this procedure (as defined in Section 10.3.3.3.2), proportion of area DPT of wounds treated in this procedure (as defined in Section 10.3.3.3.3), proportion of area FT of wounds treated in this procedure (as defined in Section 10.3.3.3.4) and type of

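### The full-thickness share in the procedure-level blood-loss imputation is computed from the deep-partial share, and correcting it still leaves three redundant depth shares if an intercept is fitted

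*SAP*

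**What the plan says.** Sections 10.3.3.3.2 to 10.3.3.3.4 of the SAP define three area-weighted depth shares per debridement procedure, all for use in the blood-loss imputation:

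- Superficial partial thickness (SPT): "Prop(SPT) = \frac{\sum_i \%SPT(W_i) * \%TBSA(W_i)}{\sum_i \%TBSA(W_i)".
- Deep partial thickness (DPT): "Prop(DPT) = \frac{\sum_i \%DPT(W_i) * \%TBSA(W_i)}{\sum_i \%TBSA(W_i)".
- Full thickness (FT): "Prop(FT) = \frac{\sum_i \%DPT(W_i) * \%TBSA(W_i)}{\sum_i \%TBSA(W_i)".

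The legend under the third formula explains a symbol %FT(W_i), which "is the percent area of FT of target wound i". That symbol does not occur in the formula above it.

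Section 10.1.1.3 then regresses procedure-level blood loss on wound area, all three shares and type of procedure, separately by treatment group. The FT covariate is listed as "proportion of area FT of wounds treated in this procedure (as defined in Section 10.3.3.3.4)"; the SPT and DPT covariates are listed in the same way, each pointing to its own formula. The section names no reference share and does not say whether there is an intercept. For each of 25 imputations, a coefficient vector is drawn from its sampling distribution, predictions are computed from it, and a normal residual is added.

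**The concern.** There are two linked faults. The first is the formula: taken literally, the variable called Prop(FT) carries no full-thickness information. The second is the model: the three shares are linearly dependent, so the coefficients to be drawn have no unique estimate and X'X has no ordinary inverse.

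Blood loss is one of the four endpoints in the testing hierarchy of Section 11.1.8. The imputation is fully prescribed, down to its 25 seeds (11468 to 11492), and Section 6.4 requires a second statistician to implement the secondary-endpoint analyses independently. If the handling of the redundancy is left to software defaults, two programmers can make different choices. They can then obtain different imputed values from the same seeds, even where the underlying distribution is the same. In one combination of choices the imputation model itself is wrong.

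**Working it through.** **Inputs.** The three share formulas (10.3.3.3.2 to 10.3.3.3.4), the covariate list and coefficient draw (10.1.1.3), and the composition of target-wound area as SPT plus DPT plus FT (7.3.1). The plan gives no figure to reproduce.

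**Step 1: the formula.** As printed, Prop(FT) = Σ %DPT·%TBSA / Σ %TBSA, which is exactly Prop(DPT). For a single wound of any area A that is entirely full thickness, %SPT = 0, %DPT = 0 and %FT = 100:

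- printed: 0·A / A = 0
- with %FT in the numerator: 100·A / A = 100

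**Step 2: the sum of the correct shares.** Because each wound's area is made up of the three depths,

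Prop(SPT) + Prop(DPT) + Prop(FT) = Σ (%SPT + %DPT + %FT)·%TBSA / Σ %TBSA = 100·Σ %TBSA / Σ %TBSA = 100.

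**Step 3: rank of the design.** The covariates are wound area, three shares and type of procedure (5 columns), plus an intercept if fitted (6 columns).

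| Formula | Intercept | Columns | Rank | Linear dependence |
|---|---|---|---|---|
| As printed | yes | 6 | 5 | FT column = DPT column |
| As printed | no | 5 | 4 | FT column = DPT column |
| Corrected | yes | 6 | 5 | SPT + DPT + FT = 100 × intercept |
| Corrected | no | 5 | 5 | none |
| Two shares only (FT omitted in the check) | yes | 5 | 5 | none |

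Correcting the numerator is therefore not enough when an intercept is fitted. Omitting one share as well restores full rank.

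**Step 4: effect on the imputations.** The drawn coefficients are used only to form predictions. With an intercept, the true FT share is 100 − Prop(SPT) − Prop(DPT), so the intercept, SPT and DPT columns already contain it. The rows to be imputed obey the same constraint, so their predictions are determined even though the individual coefficients are not.

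This was checked on 120 simulated procedures with one to three wounds each. The data were invented for illustration, and blood loss was made to depend on the FT share.

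- With an intercept, the residual SD was 153.89 under the printed formula, the corrected formula and the model without FT. Fitted values and prediction variances also agreed.
- Without an intercept, the corrected formula again gave 153.89, but the printed formula gave 174.30, a ratio of 174.30 / 153.89 = 1.13. Here the FT information is lost.

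The 13% applies only to these simulated data and does not estimate the effect in the trial.

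**The case against.** The strongest reply is that this is a one-symbol slip that the surrounding text corrects. The heading, the introductory sentence, the legend and the covariate name in 10.1.1.3 all point to FT, and the two preceding formulas show the pattern. A fault in the text extraction cannot be excluded for the symbol itself. Most programmers would code what was meant, and most regression software deals with a redundant column as routine. This largely stands as an account of what would happen in practice. It does not remove the contradiction inside 10.3.3.3.4, and the redundancy of the three shares with an intercept does not depend on the symbol.

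A reader might infer that the imputation cannot be carried out at all, or that imputed blood loss is wrong in any case. The documents do not support that. What lacks a unique value is the individual coefficients. With an intercept and a redundant column dropped, predictions, their variances and the residual SD are the same under the printed and the corrected formula. Singularity after correction is also conditional, because the SAP does not state an intercept and without one the corrected model has full rank.

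The reach is narrow too. Blood loss is last in the hierarchy. The whole-period imputation in 10.1.1.3 uses wound area, categorical depth and course of debridement, not these shares. The version with fewer missing values becomes the main analysis (7.3.2.2). The procedure-wise sum needs haemoglobin before and after every procedure, whereas the whole-period value needs only the first and the last. On haemoglobin alone, the procedure-wise version cannot be complete for more patients, so it is likely to be supportive. A tie, or missing transfusion data, could change that.

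**Conclusion.** The point holds in limited form. Section 10.3.3.3.4 states a formula that contradicts its own heading and legend, and 10.1.1.3 enters three shares of which one is redundant if the model has an intercept. As printed, the design is singular with or without an intercept; corrected, it is singular only with one.

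The effect on imputed blood loss depends on coding choices that the SAP leaves open:

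- **Intercept fitted, redundant column dropped:** the distribution of imputed values is unchanged.
- **No intercept, formula coded literally:** full-thickness information is lost and the imputation model is wrong.

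This rests on two assumptions: that the three depth percentages of each target wound add to 100, as the area definition in 7.3.1 implies, and that the formula in the source document reads as reproduced here. It is a minor correction confined to the procedure-level imputation. It gives no ground for doubting the primary endpoint or the whole-period blood-loss analysis.

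**What to change.** In 10.3.3.3.4, replace %DPT(W_i) by %FT(W_i) in the numerator. In 10.1.1.3, state that the procedure-level model has an intercept and enters only two of the three shares, for example DPT and FT with SPT as reference. The choice of reference does not alter the distribution of the predictions, but it should be named so that both programmers use the same model with the fixed seeds. The cost is one symbol and one phrase; no data collection, sample size or other analysis changes.

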10.3.3.3.5. Course of debridement procedure

For the multiple imputation outlined in Section 10.1.1.3 for each patient a categorical variable describing the course of the debridement process will be calculated. The different levels of the variable are defined as:

- Only non-surgical SOC debridement
- Non-surgical SOC debridement followed by surgical debridement
- Only surgical debridement
- Only NexoBrid debridement
- NexoBrid debridement followed by non-surgical SOC debridement followed by surgical debridement
- NexoBrid debridement follow by surgical debridement
- Only Gel Vehicle debridement
- Gel Vehicle debridement followed by non-surgical SOC debridement followed by surgical debridement
- Gel Vehicle debridement followed by surgical debridement

10.3.4. Safety Endpoints

10.3.4.1. Safety Endpoint: Time to reach complete wound closure

Information about date will be transformed to time in days from randomization. Time until complete wound closure (for definition see Appendix 13.1.1), will be defined as the time (in days) until complete wound closure has been achieved at a wound level. For wounds, which do not reach complete wound closure, the time will be censored at last date of wound closure assessment.

10.3.4.2. Safety Endpoint: Cosmesis and function at 12 months from wound closure

MVSS sub scores at 12 months for pigmentation, pliability, height, vascularity, pain and pruritus will be added up to obtain the overall MVSS score (range 0 to 18) at 12 months per target wound. The patient MVSS score will be the average of the MVSS over all TWs. Additionally, the average MVSS score for donor site scars will be calculated per patient.

10.3.4.3. *Safety Endpoint: Cosmesis and function at 24 months from wound closure*

MVSS sub scores at 24 months for pigmentation, pliability, height, vascularity, pain and pruritus will be added up to obtain the overall MVSS score (range 0 to 18) at 24 months per target wound. The patient MVSS score will be the average of the MVSS over all TWs. Additionally, the average MVSS score for donor site scars will be calculated per patient.

10.3.4.4. *General Parameters of safety*

Volume of blood transfusions given

The volume of blood transfusions given during hospitalization will be computed for each patient as $V_{WB} + \frac{5}{3}V_{PC}$, where V_{WB} and V_{PC} are the volume (in milliliters) of whole blood and packed red blood cells transfused. As in the calculation of blood loss in Section 10.3.3.3.1, the factor of 5/3 is derived from chapter 5 of Transfusion Medicine, 4th Edition [31] and compensates for the fact that equal volumes of whole blood and packed red blood cells are not comparable.

The volume of blood transfused will be calculated overall, as well as separately for volumes transfused before start of treatment, during the ER period, within 1 week after the ER period and later than 1 week after the ER period for each patient.

Extent of analgesia, anesthesia and antibiotic use

The numbers and percentages of patients per each level of sedation (see definitions in Appendix 13.1.2) per procedure (in topical arms: 1st and second topical application, surgical rescue procedures and non-surgical rescue procedures; in SOC arms: surgical procedures and non-surgical procedures) will be calculated.

The number of days of exposure to antibiotic drugs will be calculated for each patient. This will be done overall, for antibiotic use due to AE involvement (as indicated in the eCRF) and for prophylactic antibiotic use (as indicated in the eCRF) separately.

Incidence of increased interstitial/compartment syndrome

For each patient in the topical arms a binary (yes/no) variable is indicating whether the patient developed a burn-induced compartment syndrome (BICS) during the eschar removal procedure is given in the data.

Incidence of QT prolongation

Incidence of QT prolongation will be analyzed separately. The analysis and all needed transformations are described in a separate document.

Rates of hospital readmission

For each hospital readmission, a binary (yes/no) variable will be computed indicating whether this readmission was planned or not. A readmission will be considered as being planned when the reason for readmission was indicated as “planned wound management” or “scar modulation” in the eCRF. Readmissions for which the reason was given as “AE” in the eCRF are considered as being unplanned. Hospital readmission for which the reason is given as “other” will be reviewed by blinded personnel of the sponsor in order to decide whether they are to be classified as planned or unplanned.

For each patient a binary (yes/no) variable will be computed indicating whether this patient had a hospital readmission or not. Furthermore, a variable giving the number of planned hospital readmissions and a variable giving the number of unplanned readmissions will be computed for each patient.

Relative and absolute frequencies of hospital readmission will be calculated per treatment arm.

Change in PTT/INR

Change in PTT/INR will be computed as change from pre Eschar Removal procedure to 4h ± 15 min post first application (Topical arms) respectively to 4h post first SOC treatment (SOC arm) for each patient. Additionally, change from baseline PTT/INR will be computed for the first and second daily assessment post treatment (24h & 48h after start of debridement).

The proportion of patients with a change to > upper limit of normal range PTT/INR (patients with normal PTT/INR at baseline and PTT/INR > upper limit of normal range at the respective time point) will be computed per treatment arm and time point of measurement (4h post treatment, 24 h, 48h). Reference count is the number of patients with normal PTT/INR values at baseline. For the classification of normal and abnormal PTT/INR values, the reference limits of the local labs will be used.

Change in blood glucose

Change in blood glucose will be computed as change in blood glucose value from pre first topical procedure to 4h post first topical procedure (4h after removal of topical) and from

post first topical to post second topical (if available) and from pre surgical procedure to post surgical procedure for each patient. In case non-surgical procedure was the only one performed for a SOC patient, the change in blood glucose value will be computed as change from pre to post procedure. Furthermore, a binary (yes/no) variable will be computed indicating whether there was a change to above upper limit of normal (the upper reference limit of the central lab) from baseline to 4h post treatment for each debridement procedure. This is the case if the blood glucose level at baseline was below the upper limit of the normal range as given in the data base and was above the upper limit at 4h post treatment. From this for each patient a binary variable will be computed indicating whether there was a change in blood glucose to > upper limit of normal range at any of the debridement procedures.

Lower Extremity Function Scale (LEFS)

The LEFS consists of 20 items which can each be answered on a scale of 0 to 4. In the database the answers will be coded as 1 to 5. Therefore, the total LEFS for a patient will be computed as

$$LEFS = \sum_{i=1}^{20} a_i - 20,$$

where a_i is the answer to item i (coded 1 to 5).

Disabilities of the Arm, Shoulder and Hand (QuickDASH)

The QuickDASH consists of 11 items which are scored 1-5. At least 10 of the 11 items must be completed for a score to be calculated. The assigned values for all completed responses are simply summed and averaged, producing a score out of five. This value is then transformed to a score out of 100 by subtracting one and multiplying by 25. Hence, the QuickDASH score for a single patient is calculated by:

$$QuickDASH = \left(\frac{\text{sum of } n \text{ responses}}{n} - 1 \right) * 25.$$

Range of Motion (ROM)

For each visit (12 months FU and 24 months FU), a binary (yes/no) variable is given in the eCRF, indicating whether the range of motion assessment for that patient was abnormal or not. Furthermore, for each visit (12 months FU and 24 months FU) a binary (yes/no) variable

will be computed, indicating whether there was at least one abnormal (NCS) ROM assessment for that patient. Finally, for each visit (12 months FU and 24 months FU) a binary (yes/no) variable will be computed, indicating whether there was at least one abnormal (CS) ROM assessment for that patient.

EQ-5D (Quality of Life)

EQ-5D consists of 5 items with 3 possible answers each. It will be evaluated per the EQ-5D-3L user guide [32].

For each item relative and absolute frequencies of the answers will be computed in total and per age group defined in the EQ-5D-3L user guide per treatment arm and overall. Furthermore, summary statistics of the EQ VAS will be computed in total and per age group defined in the EQ-5D-3L user guide per treatment arm and overall.

The EQ-5D states will be converted to a single summary index as described in the EQ-5D-3L user guide.

Burn Specific Health Scale – Brief (BSHS-B)

The Burn Specific Health Scale – Brief (BSHS-B) consists of 40 item which can each be scored with 0 – 4. In the dataset the scores will be coded as 1- 5. The 40 items can be aggregated to 9 domains. The domains are:

- Heat sensitivity (questions 28-32 of the eCRF)
- Affect (questions 10-16 of the eCRF)
- Hand Function (questions 4-8 of the eCRF)
- Treatment Regimens (questions 33-37 of the eCRF)
- Work (questions 9, 38-40 of the eCRF)
- Sexuality (questions 21-23 of the eCRF)
- Interpersonal Relationships (questions 17-20 of the eCRF)
- Simple Abilities (questions 1-3 of the eCRF)
- Body Image (questions 24-27 of the eCRF)

For each domain a domain specific sub score is computed using the following formula:

$$Score(Domain) = \frac{1}{n} \sum_{i=1}^n (Score_i - 1),$$

where n is the number of items of the domain and $Score_i$ is the score of the i th item as coded in the data set (i.e. the domain score is the mean of the item scores as coded in the BSHS-B).

An overall BSHS-B score is computed as the mean of the domain specific sub scores.

Immunogenicity evaluation

The immunogenicity evaluation will be done in a separate analysis and is described in a separate document.

Pyrexia and hypothermia

Pyrexia (and related terms) and hypothermia reported as AEs will be presented in the AEs tables.

Systemic Infection

For each patient a binary (yes/no) variable will be computed indicating whether the patient developed a systemic infection during the study. For data captured with the eCRF version from 13 Oct 2016 the information, whether an AE is a systemic infection, is directly available in the AE description. For data captured before that, a medical person appointed by the sponsor will review all MedDRA Preferred Terms belonging to the MedDRA SOC of “Infections and Infestations”, as well as all other Preferred Terms reported in the study, and all reported terms of AEs including the word “infection”, to decide which AEs meet the definition of systemic infection.

Systemic adverse events

Counts and frequencies of systemic adverse events (marked as “general” in the eCRF) per treatment will be computed. This will be done separately by:

- System organ class
- Preferred term
- Severity (mild / moderate / severe AEs)
- Relatedness (not related / remotely related / possibly related / probably related / related AEs)

- Time of onset (before treatment / during the treatment session / during the first week after treatment / during week 2 to week 4 after treatment / during week 5 to week 8 after treatment / more than 8 weeks after treatment)

For each of the tree stages of analysis (see Section 11 for details), the safety data gathered in that stage will be analyzed separately. That is, in the acute stage analysis, all AEs reported until the 3 months follow-up will be analyzed. In the second stage analysis (12 months follow-up), all AEs reported between the 3 months follow-up and the 12 months follow-up (including AEs from first stage that are still ongoing) will be analyzed. Analogously, in the third stage analysis (24 months follow-up), all AEs reported between 12 months follow-up and the 24 months follow-up (including AEs from the first or second stage that are still ongoing) will be analyzed.

Local adverse events

Local adverse events are classified as being local – TW related or local – not TW related in the eCRF. Per each of these categories, counts and frequencies of adverse events per treatment group will be computed. This will be done separately by:

- System organ class
- Preferred term
- Severity (mild / moderate / severe AEs)
- Relatedness (not related / remotely related / possibly related / probably related / related AEs)
- Time of onset (before treatment / during the treatment session / during the first week after treatment / during week 2 to week 4 after treatment / during week 5 to week 8 after treatment / more than 8 weeks after treatment)

For each of the tree stages of analysis (see Section 11 for details), the safety data gathered in that stage will be analyzed separately. That is, in the acute stage analysis, all AEs reported until the 3 months follow-up will be analyzed. In the second stage analysis (12 months follow-up), all AEs reported between the 3 months follow-up and the 12 months follow-up (including AEs from the first stage that are still ongoing) will be analyzed. Analogously, in the third stage analysis (24 months follow-up), all AEs reported between 12 months follow-up and the 24 months follow-up (including AEs from the first or second stage that are still ongoing) will be analyzed.

Vital signs

Body temperatures given in °F will be transformed to °C using the following formula:

$$Temperature[^\circ C] = \frac{5}{9}(Temperature[^\circ F] - 32)$$

Differences in the vital signs assessments (body temperature, heart rate, respiratory rate, systolic blood pressure, diastolic blood pressure) between daily visits will be calculated by

$$Diff_d = VS_{d-1} - VS_d$$

where VS_d is the vital sign assessment at day d (daily follow-up) and d is varied from 2 to 7. Furthermore, pre-post differences for vital signs assessments per procedure will be calculated in the same way, using the screening assessment as pre first procedure and the post first procedure measurement as pre second procedure measurement if needed.

Pain assessment

For each eschar removal procedure and each daily follow-up pain assessment the change in pain from baseline will be calculated as

$$Diff_d = Pain_{Base} - Pain_d$$

where $Pain_d$ is the pain assessment at the respective time point. For the calculation of the difference in pain for the eschar removal procedures the pain assessment post that procedure will be used.

